1.0 Objectives / Specific Aims

Specific aims: Smoking cessation and relapse prevention represent an important opportunity to improve cancer survival rates (1, 2), reduce the risk of cancer treatment complication (3), and improve the quality of life of patients with and survivors of cancer (4). Previous studies showed that repetitive TMS (rTMS) reduced cue craving to smoking and treat nicotine dependent smokers (5, 6). Recently one study completed by our team demonstrated that 10 sessions of rTMS over the left dorsolateral prefrontal cortex (DLPFC) reduced cigarette consumption and cue craving, and also increased quitting rate on target quit date in nicotine dependent smokers. Thus, we propose conducting a controlled, double-blind trial comparing the effect of treatments of active rTMS and sham rTMS on cigarette abstinence days, cigarette consumption and smoking craving during a 7-days of quit attempt period in 20 nicotine-dependent patients with cancer. Specific aims are: Aim 1: Assess a feasibility of the rTMS for smoking cessation in cancer patients. Aim 2: Obtain preliminary estimates of whether one-week active rTMS of left DLPFC tends to be more efficacious than sham rTMS during a 7-days of quit attempt laboratory model period increasing abstinence days, and also decreasing cigarette consumption and cue-elicited craving in cancer patients with smoking.

1.1. Primary objective

To assess a feasibility of the rTMS for smoking cessation in cancer patients: The primary feasibility measures are (1) whether or not we can enroll 20 cancer patients with smoking within 12 months? (2) Study attrition. How many subjects can complete 7-day quit attempt during rTMS treatment? How many subjects will complete one-month follow-up? (3) To measure the percent completion of assessment measures.

1.2 Secondary objectives

To obtain preliminary estimates of whether one-week active rTMS of left DLPFC tends to be more efficacious than sham rTMS during a 7-days of quit attempt laboratory model period increasing abstinence days, and also decreasing cigarette consumption and cue-elicited craving in cancer patients with smoking.

1.3 Exploratory objectives

Self-reported number of cigarettes smoked per day, cue-induced craving (QSU – Brief), visual analog scale for craving and side effect will be measured pre and post each rTMS session. Other assessment, Carbon Monoxide, Fagerstrom Test for Nicotine Dependence (FTND), and MNWS-R will be completed at baseline and the last TMS. Quitting attempt will verify daily CO < 5 ppm. FTND, Feasibility metrics will also be tracked, including numbers of complete TMS sessions and dropout rate.

2.0 Background

2.1. Smoking Cessation after Cancer

The benefits of smoking cessation after a cancer diagnosis are overlooked. In many high-income countries, cancer survival has improved over the last few decades (1). About half of patients with cancer are now expected to survive their cancer for at least 10 years after diagnosis (2). However, many people with cancer still continue to smoke despite smoking being a known and often reversible cause of premature death as a result of cancer, cardiovascular, respiratory, and several other diseases (4). In addition, continued smoking after a cancer diagnosis increases the risk of second primary tumors and cancer recurrence and it a cause of treatment complications (5). Smoking cessation after a diagnosis imparts significant survival benefits for people with cardiovascular disease,

diabetes, and multiple sclerosis (6). That is, all-cause mortality among cancer survivors who continue to smoke after a diagnosis is significantly worse than those who have never smoked (1).

2.2. Smoking Cessation for Cancer Patients

In 2008, when the US department of Health and Human Services treatment guidelines for tobacco cessation were last updated, 10 specific recommendations for treatment were formulated as a quick guide to the overall principles (7). While some patients may quit on their own or require minimal advice to quit, it is essential to keep in mind that the treatment of tobacco use in many patients with cancer may require a more intensive and comprehensive approach (2-5). Unfortunately, very few smoking cessation studies have been conducted in the cancer setting, and their focus is usually on the delivery of behavioral intervention rather than the effectiveness of a specific therapy or pharmacotherapy (8, 9). Likewise, patients with cancer are usually excluded from pharmacologic smoking cessation trials, mostly owing to concerns about the patients' ability to participate in and complete a trial and the difficulty of determining whether any emerging side effects are due to the cancer or cancer treatment or to a smoking cessation medication.

2.3. Transcranial Magnetic Stimulation for Smoking Cessation

To date, several human studies have begun to evaluate the effects of rTMS applied to the lateral or medial prefrontal cortex on cue-induced craving and cigarette consumption (5, 10-12). In one previous study, experimenters (10) administered high frequency rTMS to the left DLPFC of treatment-seeking smokers. Subjects received 20 trains of either real or sham rTMS (20Hz, 90% motor threshold, 2.5 secs-on, 42.5 sec intertrain intervals for a total of 1000 pulses) over the left prefrontal cortex. These investigators found that while real rTMS was associated with significant reduction in terms of the number of cigarettes smoked in comparison with sham stimulation ($p < .01$), levels of craving did not differ significantly between the groups. In contrast, Amiaz and colleagues reported that rTMS (100% rMT, 10Hz, 20 train/day, total 1000 pulses) of the DLPFC reduced both cigarette craving and consumption (5). One study has recently completed a preliminary parallel-groups sham-controlled trial of rTMS in combination with the nicotine patch to treat tobacco addiction in heavily-dependent patients with schizophrenia (13). They found that rTMS did not increase abstinence rates, but did significantly reduce tobacco cravings induced by short-term (30-60 minutes) abstinence, which was assessed before application of the nicotine patch. Recently Dinur-Klein and colleagues reported that deep rTMS of the prefrontal and insular cortices reduced cigarette consumption and nicotine dependence (14). A recently completed exploratory study led by the PI used a controlled, double-blind method to compare the impact of daily treatments of active rTMS (delivered to DLPFC) vs sham rTMS on cue craving and cigarette consumption in nicotine-dependent cigarette smokers. We found that 10-sessions of rTMS significantly reduced cigarette consumption and cue craving compared to sham stimulation. These studies suggest that high frequency rTMS delivered over the left DLPFC can be able to attenuate nicotine consumption and craving. However, to date, no study has been reported to use rTMS smoking cessation for cancer patients. **As such, TMS research of smoking cessation for cancer patients are greatly needed in future.**

2.4. The 7 Days of a Quit Attempt Laboratory Based Model

Recent medication screening paradigms have focused on the first 7 days of a quit attempt to evaluate treatment efficacy, because the early abstinence is a vulnerable time for most smokers (15, 16). Each year, 40% of smokers try to quit, but 50% to 75% relapse within the first week of a quit attempt (17). Furthermore, withdrawal symptoms peak during the first few days of abstinence (18, 19), and these symptoms, in turn, predict relapse (20). These laboratory-based models of medication screening provide smokers with medication and assess the number of days of abstinence during a 7-day simulated quit attempt as the primary end point. As such, we will perform the 7 days of abstinence attempt laboratory model for the rTMS study in smokers. Furthermore, Perkins and colleagues have reported that crossover design with laboratory model of 7 day abstinence attempt has improved the efficacy of initial tests in smoking cessation for efficacy in smoking cessation drug discovery (15, 16, 21-23).

3.0 Intervention to be studied

Transcranial magnetic stimulation (TMS) is a noninvasive (and relatively painless) brain stimulation technology that can focally stimulate the brain of an awake individual (24, 25). A localized pulsed magnetic field transmitted through a TMS coil is able to focally stimulate the cortex by depolarizing superficial neurons (26, 27) inducing electrical currents in the brain (28). If TMS pulses are delivered repetitively and rhythmically, the process is called repetitive TMS (rTMS). rTMS for the treatment of depression was approved for one manufacturer by the U.S. Food and Drug Administration (FDA) in October, 2008 (29, 30) and for a different device in January 2013. Researchers are investigating rTMS potential treatment effects in other neuropsychiatric disorders (schizophrenia, pain, alcohol, cocaine, stroke) (31)Treatment parameters and grouping – The time in the chair and the number of pulses on the head will be the same for all subjects. Active or sham TMS will be the only difference. The sham group only receives sham at all treatments. Stimulation frequency for all active subjects: 10 Hertz – Pulse train duration (on time) 5 seconds, Inter-train interval (off time) 10 seconds (15 second cycle time), Power (intensity) level 100% rMT, Total 60 trains, 15 minutes, Total pulses 3000 per day, $3000 \times 10 = 30000$ pulses for 10 sessions.

The sham TMS system will be connected to an electrical generator on a 9 V battery and electrodes will be placed over the prefrontal cortex. The regulator is triggered by the TMS machine to allow brief, microsecond, pulses of the electrical current through to the skin on the subjects' forehead. Electrical stimulation will be triggered by the TMS machine to correspond to the sham TMS pulses. To further assess the adequacy of the mask, TMS administrators, clinical raters, and patients will complete "best guess" questionnaires, assessing their best guess as to treatment condition, and their level of confidence in this guess.

4.0 Study Endpoints

4.1 Primary efficacy endpoint

Conducting feasibility includes: (1) how many cancer patients with smoking can be enrolled in 12 months. (2) Study attrition. How many subjects can complete 7-day quit attempt during rTMS treatment. How many subjects will complete one-month follow-up. (3) Measurement strategy- percent completion of assessment measures.

4.2 Secondary efficacy endpoints

Total number of smoke-free days during a 7-day quit attempt. Self-reported abstinence during the 7-day quit attempt will be assessed via timeline. The maximum number of consecutive days of abstinence will be recorded. Participants who does not report at least one 24-hour period of abstinence will be recorded as "0" days abstinent.

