4.3. Exploratory endpoints

Self-reported_number of cigarettes smoked per day, cue-induced craving (QSU – Brief), visual analog scale for craving and side effect will be measured pre and post each rTMS session. Other assessment, Carbon Monoxide, FTND, and MNWS-R will be completed at baseline and the last TMS. Quitting attempt will verify daily CO < 5 ppm. FTND, Feasibility metrics will also be tracked, including numbers of complete TMS sessions and dropout rate.

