10.2 Baseline Evaluation

After the informed consent is obtained, participants will be assessed for study inclusion/exclusion criteria.

(1) Demographic Data: Basic demographic information including age, gender, race, and medical history will be collected. (2) Mini International Neuropsychiatric Interview (MINI) (32): This is a well-standardized structured instrument used to provide quick and accurate DSM-IV psychiatric diagnoses. The MINI will be used to confirm the inclusionary/exclusionary diagnoses in the participants. (3) Tobacco Use History: Detailed history of current and past tobacco use will be obtained, including cigarette smoking. The questions addressed will include the amount, frequency, duration of smoking, preferred brand, reasons for smoking, smokeless tobacco, family history, etc. (4) Fagerstrom Test for Nicotine Dependence (FTND)(33): This is a self-rating questionnaire for nicotine dependence. (5) Questionnaire of Smoking Urges- Brief (QSU-B) (34): This is a 10-item self-rating questionnaire for assessment of craving. (6) Minnesota Withdrawal Scale - Revised (MNWS-R) (35): MNWS-R is a DSM-IV based instrument to assess symptoms of nicotine withdrawal. (7) Biomarkers: We will also use carbon monoxide (CO) level in the expired air by a standard CO breathalyzer at each visit. (8) Tobacco diary: This is a daily diary of all tobacco products consumed in the period between visits,

including cigarettes. Participants will maintain a daily tobacco diary, which will be collected at each visit.

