12.2 Data analysis

General considerations: All data will be analyzed in consultation ([name]) with the electronic system called REDCap (Research Electronic Data Capture). Statistical analyses will be performed using SPSS 22.0 (IBM Inc.). Baseline demographic and baseline characteristics, together with safety analyses will be performed on all enrolled subjects. Baseline values are defined as the measures on screening visit. The standard summary statistics for continuous variables are: mean, standard deviation, median, minimum and maximum. The standard summary statistics for categorical variables are: count and percentage. All statistical tests will be two-sided. For comparison of means (continuous variables), the two-sample t-test or the Wilcoxon rank sum test will be used as appropriate. For comparison of proportions (discrete data), the Chi-squared test will be used as appropriate. All test performed at significance $\alpha = 0.05$.

To assess a feasibility of the rTMS for smoking cessation in cancer patients: The numbers of subjects who were randomized and who entered and completed each visit of the study will be provided, as well as the reasons for all post-randomization discontinuations, grouped by treatment and by major reason. The discontinued subjects, protocol deviations, and subjects excluded will be provided as well.

To obtain the secondary estimates: The abstinence days, and cigarette consumption and cue-elicited craving will be compared between the active TMS and sham groups with a t-test or a repeated measures analysis of covariance model. Baseline daily number of cigarettes smoked, sex and center will be used as covariates.

To analyze the exploratory measures: cue-induced craving (QSU – Brief) and visual analog scale for craving will be measured pre and post each rTMS session. Other assessment, Carbon Monoxide, FTND, and MNWS-R will be compared between two groups.

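### Smoke-free days are scored from timeline self-report, and the plan never links its own CO check or daily diary to that count

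*Combined protocol and SAP*

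**What the plan says.** Section 4.2 defines the endpoint as "Total number of smoke-free days during a 7-day quit attempt" and names its data source: "Self-reported abstinence during the 7-day quit attempt will be assessed via timeline". Its rule for zero days also depends on what the patient reports: "Participants who does not report at least one 24-hour period of abstinence will be recorded as '0' days abstinent". A second summary of the same days follows: "The maximum number of consecutive days of abstinence will be recorded". Neither CO nor the diary appears in 4.2.

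Biochemical verification appears under the exploratory headings only (1.3 and 4.3): "Quitting attempt will verify daily CO < 5 ppm". That sentence concerns the quit attempt as a whole. It does not mention the score of a day, or what follows from a failed or missing reading.

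The diary is described in 10.2: "Participants will maintain a daily tobacco diary, which will be collected at each visit". No section connects it to the timeline or to the count.

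In the analysis text, 12.1 plans Poisson or negative binomial regression for abstinent days, and 12.2 plans a t-test or repeated measures analysis of covariance. Neither has a rule for discordant sources. CO enters 12.2 only as an outcome in its own right: "Other assessment, Carbon Monoxide, FTND, and MNWS-R will be compared between two groups".

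**The concern.** The protocol uses CO to confirm smoking at entry (section 5.0, inclusion criterion 3, above 5 ppm) and says that CO will verify quitting. Yet the section that defines the outcome counts days without it. Take a patient whose timeline shows no smoking for a day, whose diary shows 2 cigarettes for the same day, and whose CO at the end of it is 9 ppm. Applied literally, 4.2 scores that day as smoke-free, although two other planned sources contradict it.

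The estimate of efficacy is at stake. If one analyst applies 4.2 literally and another lets the sentence in 4.3 govern, they obtain different counts from the same data, and the choice could be made after the data are seen. The same count feeds the hypothesis in 12.1 that quit days predict longer-term effect. Over-reporting is plausible, because 10.4 has patients told to hold out for as long as possible. A patient who guesses the assigned arm could also report differently.

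**Working it through.** The plan states no figure to reproduce: section 6.0 gives 20 patients without an effect size, standard deviation or power. The check has two parts.

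**1. How many quit-attempt days could a CO reading bear on?** The quit attempt starts after TMS 1 (10.4) and lasts 7 days, with five sessions in the treatment period (4.4). TMS 2 to 5 therefore fall inside it. The documents hold four versions of CO timing:

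- daily: the verification sentence in 1.3 and 4.3;
- baseline and last session: the same two sections, "Carbon Monoxide, FTND, and MNWS-R will be completed at baseline and the last TMS";
- each visit: 10.2, item 7;
- one mark in the 10.5 calendar, which appears to sit under baseline. The table was read from PDF, so its column position is not certain.

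The diary has a similar conflict: daily in 10.2, one mark in the calendar.

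**2. How much could the count be overstated?** Assumptions, none of them from the documents: a mean of 4 reported smoke-free days, spread evenly over the 7 days, and 10% to 30% of the CO-covered reported days contradicted.

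Overstatement = 4 × (covered days / 7) × share contradicted.

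| CO timing | Covered days | Covered reported days | Overstatement at 10% | At 30% |
|---|---|---|---|---|
| Calendar only | 0/7 = 0% | 0 | 0 | 0 |
| Last session only | 1/7 = 14% | 0.57 | 0.06 | 0.17 |
| Each visit | 4/7 = 57% | 2.29 | 0.23 | 0.69 |
| Daily | 7/7 = 100% | 4.00 | 0.40 | 1.20 |

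These figures cover only the part that CO could detect. A zero in the first row means that CO would remove nothing, not that every report is accurate. Contradictions found only in the diary would come on top.

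The table concerns a mean, not the arm difference. If both arms are overstated by the same number of days, the difference is unchanged. If one arm were at 10% and the other at 30%, with CO at each visit and 4 reported days in both, the difference would be off by 0.69 − 0.23 = 0.46 day. With 10 patients per arm (assumed, since no allocation ratio is given), each reclassified day moves an arm mean by 1/10 = 0.1 day.

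**The case against.** The strongest reply is that the protocol does intend verification. Sections 1.3 and 4.3 both say so, and an ordinary reading is that CO checks the reported abstinence. Section 4.2 names a source and excludes no other. A reader might infer that the plan bars CO or the diary from overruling the patient, or rests on self-report by design. The documents do not support that: they are silent on discordance and leave two statements unreconciled. This part of the reply stands. It does not supply the missing rule, because the verification sentence is attached neither to the endpoint nor to a day's score.

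A reader might also infer that CO and diary data will be in hand for every day. They may not be, given the conflicting schedules.

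Two arguments about harm are weaker than they look. Nothing in the documents shows that over-reporting is common, or that it would push both arms towards the maximum of 7; section 2.4 cites relapse of 50% to 75% within the first week. And the effect of guessing the arm can be examined, since 3.0 and 10.3 plan an active sham and best-guess questionnaires.

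A combined rule can also misclassify. A visit reading is not naturally tied to one calendar day: a patient abstinent yesterday who smoked this morning could fail. Days with a reading face a stricter test than days without, so the count comes to depend on attendance, which may differ by arm. The diary may not be independent of the timeline either. The fix has to deal with the first two points explicitly.

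**Conclusion.** The point holds as a gap between sections. The smoke-free-day count is defined by timeline self-report, the protocol's own CO standard and daily diary are not linked to it, and no rule covers discordant or missing readings. Applied as written, 4.2 keeps days that the other sources contradict.

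The size cannot be determined from the documents. The range of 0 to 1.2 days per patient reflects both the assumed contradiction rates and the unresolved CO schedule. The each-visit figure of 0.23 to 0.69 day is one case within it, and the direction of any bias in the arm difference is unknown.

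The stakes are moderate. Sections 4.1 and 4.2 make feasibility primary and abstinence days secondary, for preliminary estimates. The calendar in 10.5 labels abstinence days the primary outcome, which is a separate inconsistency.

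**What to change.** 1. In 4.2, count a day as smoke-free only if the timeline and the diary both show no cigarettes and, where a CO reading covers that day, the reading is below 5 ppm. State that a reading judges the 24 hours before it, with quit-attempt days cut accordingly, and that days without a reading are scored on timeline and diary. Apply the same day scores to the total and to the longest run.
2. Use this count for the arm comparison in 12.1 and 12.2. Report the timeline-only count as a sensitivity result. Report the number of CO-covered days by arm, because coverage depends on attendance.
3. Align 1.3, 4.3, 10.2 and the 10.5 calendar on when CO and the diary are collected, following the each-visit collection in 10.2.

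The cost is a change of endpoint wording and a scoring rule; no procedure is added beyond what 10.2 describes. The abstinence count will be slightly lower, and days without a visit remain self-reported.

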4.3. Exploratory endpoints

Self-reported_number of cigarettes smoked per day, cue-induced craving (QSU – Brief), visual analog scale for craving and side effect will be measured pre and post each rTMS session. Other assessment, Carbon Monoxide, FTND, and MNWS-R will be completed at baseline and the last TMS. Quitting attempt will verify daily CO < 5 ppm. FTND, Feasibility metrics will also be tracked, including numbers of complete TMS sessions and dropout rate.

4.4. Follow-up

The treatment period of the study will conclude on the end of 5-treatment during 7-day quit attempt days. Participants will then enter the follow-up phase of the study. The one follow-up phone call will happen after 1 month of the last rTMS session. Cigarette consumption will be evaluated by asking: 'how many cigarettes do you now smoke on an average day?' Craving will be assessed by asking: 'how much do you want to smoke a cigarette right now on a scale from 1 to 10?' Nicotine dependence will be assessed by the FTND question.

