
10.4. The 7 days of a quit attempt: Participants will be asked to start a quit attempt after the first TMS session.

During the abstinence attempts, subjects will be told that you "go as long as you can without smoking". We will compare the numbers of cigarettes smoked and days of abstinence between active rTMS week and sham rTMS week.

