10.5 Study Calendar

Timepoints	Baseline	TMS 1	TMS 2	TMS 3	TMS 4	TMS 5	Follow-up
Assessments							
Informed Consent	X						
Demographic	X						
Medical history	X						
Tobacco Use History	X						
Fagerstrom Test for Nicotine Dependence (FTND)	X						
Questionnaire of Smoking Urges- Brief (QSU-B)	X						

Minnesota Withdrawal Scale - Revised (MNWS-R)	X						
carbon monoxide (CO)	X						
Tobacco diary	X						
Primary Outcome – number of abstinence days	X	X	X	X	X	X	
Secondary Outcome – cigarette per day	X	X	X	X	X	X	
Visual analog scale of craving for cigarette	X	Pre and post X					
Adverse Events		X	X	X	X	X	
Best guess		X				X	
Phone call							X

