13.0 Provisions to Monitor the Data to Ensure the Safety of Subjects

1. *Trial Management:* The study will be managed from the Brain Stimulation Lab within the Department of Psychiatry and Behavioral Sciences at the Medical University of South Carolina.
2. *Data Management and Analysis:* Data will be entered by research assistants directly into a computer using standard database software. The data analysis plan is outlined in the Data Analysis Plan section.
3. *Quality Assurance:* The PI will have weekly meetings with the research assistants to discuss qualitative comments received during data collection and any problems in data collection. The statistician will periodically examine the database to look for irregularities. Initial data analyses will examine distributions of variable scores, and comparability of baseline characteristics across conditions in case analyses need to be adjusted for these. Confidentiality protections are outlined above.
4. *Regulatory Issues:* All unexpected Adverse Events (AEs) will be reported to the MUSC IRB and Committee on Human Research within 48-business hours. Serious AEs will be reported within 24-business hours. Follow-up of all unexpected and serious AEs will also be reported to these agencies.

5. *Definition of AE and SAE:* An AE is defined as any untoward medical occurrence in a study subject administered a pharmaceutical product that does not necessarily have a causal relationship with this treatment (ICH GCP). Any unwanted change, physically, psychologically or behaviorally, that occurs in a study participant during the course of the trial is an adverse event. A Serious Adverse Event (SAE) is defined as an adverse event that has one of the following outcomes: death, life-threatening, inpatient hospitalization or prolongation of existing hospitalization, persistent or significant disability/incapacity, a congenital anomaly/birth defect.

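### No enquiry about new adverse events is scheduled after the fifth TMS session, although section 13.0 defines adverse events over the whole trial

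*Combined protocol and SAP*

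**What the plan says.** Four parts of the combined protocol and SAP bear on this point.

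- **Section 10.5, Study Calendar.** The row reads "Adverse Events X X X X X". The marks fall under TMS 1 to TMS 5, and the Baseline and Follow-up cells are empty. The only entry in the Follow-up column is the phone call.
- **Section 4.3, Exploratory endpoints.** Side effects are tied to the stimulation visits: "visual analog scale for craving and side effect will be measured pre and post each rTMS session".
- **Section 4.4, Follow-up.** "The treatment period of the study will conclude on the end of 5-treatment during 7-day quit attempt days". Then comes a single contact: "The one follow-up phone call will happen after 1 month of the last rTMS session". The listed content is consumption ("Cigarette consumption will be evaluated by asking: 'how many cigarettes do you now smoke on an average day"), a craving rating from 1 to 10, and FTND. Neither adverse events nor side effects are listed.
- **Section 13.0.** The definition has no end date short of the end of the trial: "Any unwanted change, physically, psychologically or behaviorally, that occurs in a study participant during the course of the trial is an adverse event". The section also gives staff a general duty to identify events. It requires each recorded event to be followed until it resolves, stabilises or the patient leaves the study.

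Section 12.3 plans descriptive safety summaries by group for every scheduled visit.

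**The concern.** The definition of an adverse event covers the follow-up phase, but no scheduled contact in that phase asks about one. An event that begins after TMS 5 enters the data only if the patient volunteers it. For that period an empty record could mean that nothing happened or that nobody asked, and the two cannot be told apart in either arm.

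This matters for two reasons. Section 2.3 says that no study of rTMS for smoking cessation in cancer patients has been reported, and section 15.0 allows that the procedure may have unknown side effects. The safety summary in 12.3 is meant to describe the two arms at each scheduled visit, yet it would have no solicited adverse-event data from Follow-up to describe.

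**Working it through.** The plan states no figure on this point, so there is none to reproduce. The check has three steps.

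**1. Is the gap real, or a slip in the calendar?**

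The calendar alone would be weak evidence because it is incomplete elsewhere. It shows FTND and CO at Baseline only. Yet section 4.3 has both at the last TMS visit as well, section 10.2 has CO at each visit, and section 4.4 asks FTND on the call. A blank cell in 10.5 therefore does not prove that an item is not collected.

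Two other sections point the same way. Section 4.4 itemises the call without adverse events, and section 4.3 attaches side-effect measurement to the rTMS sessions. No section schedules an enquiry about new events after TMS 5.

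**2. How long is the period without enquiry?**

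Inputs:
- D, the days spanned by the five sessions. Section 4.4 puts them within the 7-day quit attempt. Section 10.4 says "Participants will be asked to start a quit attempt after the first TMS session", so the window can run to day 7 or day 8. Consecutive daily sessions would take 5 days. I take D = 5, 7 or 8.
- F, the days from the last session to the call. Section 4.4 gives 1 month. I assume 28, 30 or 31 days.

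Share without scheduled enquiry = F / (D + F).

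| D | F = 28 | F = 30 | F = 31 |
|---|---|---|---|
| 5 | 28/33 = 84.8% | 30/35 = 85.7% | 31/36 = 86.1% |
| 7 | 28/35 = 80.0% | 30/37 = 81.1% | 31/38 = 81.6% |
| 8 | 28/36 = 77.8% | 30/38 = 78.9% | 31/39 = 79.5% |

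The range is 77.8% to 86.1%, well above half throughout. The time from consent to TMS 1 is not stated and is left out. If the sessions finish on day 5, the last 2 to 3 days of the quit attempt (7 − 5 = 2, or 8 − 5 = 3) also fall after the last scheduled adverse-event assessment.

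**3. What would a question on the call change?**

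If it covers the whole time since the last session, the share without any scheduled enquiry falls to 0% for patients who are reached. It stays as in the table for those who are not. The coverage would be retrospective.

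**The case against.** The strongest case on the other side has four parts.

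*Adverse events are still captured after TMS 5.* A reader might infer that nothing is ascertained once treatment ends, or that persistent events are lost. The documents do not support either reading. The duty in section 13.0 to identify events is not confined to TMS visits, so a spontaneous report, including one made on the call, would be recorded. Events recorded by TMS 5 are followed. Only solicitation of new-onset events is missing.

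*Section 4.4 is an endpoint paragraph.* It describes smoking outcomes and does not claim to list everything asked on the call. That is fair: its silence is not a decision to exclude adverse events. But nothing elsewhere supplies the question, and staff who follow the text would not ask it.

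*The percentage exaggerates the risk.* A reader might infer that about four-fifths of adverse events would be missed. This does not follow, because the figure is a share of days. Section 15.0 describes mainly acute or short-lived effects: seizure induced by stimulation, temporary headache, and a shift in hearing threshold lasting less than 4 hours. The documents name no delayed device effect and give no basis for an expected number of missed events in 20 patients.

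*The consequences are limited.* The primary objective is feasibility and the safety analysis is descriptive, so no primary or secondary result changes. This stands and limits the weight of the point. It does not remove the mismatch between the definition and the schedule, which is cheap to close.

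**Conclusion.** The point holds in a limited form. The plan schedules no solicitation of new adverse events after TMS 5, while section 13.0 defines adverse events over the whole course of the trial. New-onset events in about 78–86% of the time from TMS 1 to the call (81% with 7 treatment days and a 30-day month) would depend on spontaneous reporting.

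The range assumes sessions spanning 5 to 8 days and a month of 28 to 31 days. The number of events affected cannot be estimated from the documents and, given the mainly acute risks described, may be small. The change is worth making because the call already takes place and the gap leaves the by-arm safety summary without solicited data for most of the time on study.

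**What to change.** - In section 10.5, mark adverse events at Follow-up.
- In section 4.4, add to the call one open question about any new or ongoing unwanted change since the last session, plus the side-effect measure already used at the TMS visits. The documents do not describe that measure further, so it should be named.
- In section 12.3, state that Follow-up is among the scheduled visits summarised by arm. Report those data as retrospective and limited to patients reached, with the number reached in each arm.
- If the intention is instead that collection of new events ends at TMS 5, section 13.0 should say so. Either way, sections 4.4, 10.5, 12.3 and 13.0 need to agree.

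The cost is a minute or two on each existing call, one calendar mark and a sentence or two of text. No visit is added. The drawback is that answers a month later rest on recall, so mild or brief events may be under-reported.
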